## **10.8 Pharmacokinetic and Pharmacodynamic Analyses**

**For Expansion cohort no PK and PD analysis will be performed.**

### **10.8.1 Pharmacokinetic Analysis**

The PK analysis will be based on the PK analysis set. Blinatumomab serum concentration will be quantified in all patients at baseline (pre-dose) and during the first 2 treatment cycles of treatment. Non-compartmental analysis will be performed with PK data collected at different dose levels for adults and pediatrics, respectively. Phoenix WinNonlin version 6.4 software on Citrix (Pharsight®, St. Louis, MO) as part of the validated PKS system will be used for the non-compartmental analysis.

All concentration values less than the LLOQ were set to zero before pharmacokinetic analysis. Actual dose and actual sampling time will be used. Dosing interruptions or administration errors impacting blinatumomab pharmacokinetic assessments will be taken into account in the analysis. The related concentration values and estimated PK parameters will be excluded from summary statistics where appropriate.

PK parameters such as steady state concentration (Css), clearance (CL), and elimination half-life (t1/2) will be estimated for subjects who have sufficient evaluable PK data. Summary statistics, including mean, standard deviation, median (range), geometric mean and CV% of geometric mean will be computed for each pharmacokinetic parameter and grouped by dose, treatment cycle and age groups. Individual concentration-time data will be tabulated and presented graphically. Mean concentration-time profiles for each dose will be provided.

### **10.8.2 Pharmacodynamic Analysis**

The PD analysis will be based on the PD analysis set. Descriptive statistics or graphic presentation will be used for data analysis.

Lymphocyte subsets: Cell counts of each cell type tested at baseline and over time will be presented graphically. Summary statistics of cell counts may be presented if data are sufficient. Individual data will be provided as a listing.

Cytokines: Summary statistical analysis of cytokine levels (eg, IL-2, IL-4, IL-6, IL-10, TNF- $\alpha$ , IFN- $\gamma$ ) prior to treatment and during blinatumomab infusion will be provided for each sampling collection time. Maximal cytokine concentration (Cmax) of each cytokine will be summarized by descriptive statistics. Individual data will be provided as a listing.

### 10.8.3 Exposure Response Analysis

Exploratory exposure-efficacy analyses may be performed to evaluate the relationship of efficacious exposure range and corresponding dose range if data are sufficient for conducting the analysis. Exposure-safety analyses may be performed as needed to evaluate the relationship of tolerable exposure and dose ranges. A separate exposure-response analysis plan will be generated and the results will be reported separately from the CSR.

## 11. Changes From Protocol-specified Analyses

- The clarification of primary efficacy endpoint for adult subjects (both Phase 1b and Phase 2) to be CR/CRh\*. The terms of “complete remission”, “CR”, “CR/CRh\*/CRi”, “CR/CRh\*” were used interchangeably in the protocol.
- The clarification of primary efficacy endpoint for pediatric subjects to be M1 remission.
- The clarification of RFS and Duration of Response endpoints for subjects who met primary efficacy endpoint (CR/CRh\* for adult subjects and M1 remission for pediatric subjects).
- **Sensitivity analysis for MRD response and complete MRD response is not performed because main analysis has already excluded subjects without any post-baseline response assessment.**

---

**Appendix A. Eastern Cooperative Oncology Group (ECOG) Performance Status Scale**

| ECOG Performance Status Scale |   |
|-------------------------------|---|
| Grade                         | Descriptions  |
| 0                             | Fully active, able to carry on all pre-disease performance without restriction.   |
| 1                             | Restricted in physically strenuous activity, but ambulatory and able to carry out work of a light or sedentary nature (eg, light housework, office work). |
| 2                             | Ambulatory and capable of all selfcare, but unable to carry out any work activities. Up and about more than 50% of waking hours.                          |
| 3                             | Capable of only limited selfcare, confined to bed or chair more than 50% of waking hours.   |
| 4                             | Completely disabled. Cannot carry on any selfcare. Totally confined to bed or chair.  |
| 5                             | Dead  |

Source: Oken MM, Creech RH, Tormey DC et al.: Toxicity And Response Criteria Of The Eastern Cooperative Oncology Group. Am J Clin Oncol 1982; 5: 649-655

## Appendix B. Karnofsky Performance Status

| Karnofsky Performance Status Scale |   |
|------------------------------------|---|
| Grade                              | Descriptions  |
| 100                                | Normal no complaints; no evidence of disease  |
| 90                                 | Able to carry on normal activity; minor signs or symptoms of disease.               |
| 80                                 | Normal activity with effort; some signs or symptoms of disease.                     |
| 70                                 | Cares for self; unable to carry on normal activity or to do active work.            |
| 60                                 | Requires occasional assistance, but is able to care for most of his personal needs. |
| 50                                 | Requires considerable assistance and frequent medical care.                         |
| 40                                 | Disabled; requires special care and assistance.                                     |
| 30                                 | Severely disabled; hospital admission is indicated although death not imminent.     |
| 20                                 | Very sick; hospital admission necessary; active supportive treatment necessary.     |
| 10                                 | Moribund; fatal processes progressing rapidly.                                      |
| 0                                  | Dead  |

Sources: Schag CC, Heinrich RL, Ganz PA. Karnofsky performance status revisited: Reliability, validity, and guidelines. J Clin Oncology. 1984; 2:187-193.

### Appendix C. Lansky-Play Performance Status

| Lansky Play Performance Scale |  |
|-------------------------------|--|
| Grade                         | Descriptions   |
| 100%                          | Fully active, normal   |
| 90%                           | Minor restrictions in physically strenuous activity  |
| 80%                           | Active, but tires more quickly   |
| 70%                           | Both greater restriction of, and less time spent in play activity  |
| 60%                           | Up and around, but minimal active play; keeps busy with quieter activities   |
| 50%                           | Gets dressed but lies around much of the day; no active play; able to participate in all quiet play and activities |
| 40%                           | Mostly in bed; participates in quiet activities  |
| 30%                           | In bed; needs assistance even for quiet play   |
| 20%                           | Often sleeping; play entirely limited to very passive activities   |
| 10%                           | No play; does not get out of bed   |
| 5%                            | Unresponsive   |
| 0%                            | Dead   |

Source: Biomedical Data Stewardship, Version 5, 20 Mar 2015

**Appendix D. Handling of Dates, Incomplete Dates and Missing Date**

The following data will be imputed using the following algorithm:

Adverse Events

Concomitant Medications

**Table 7. Imputation Rules for Partial or Missing Start Dates**

| Start Date         |                                  | Stop Date                 |                           |                                     |                                     |                                   |                                   | missing |
|--------------------|----------------------------------|---------------------------|---------------------------|-------------------------------------|-------------------------------------|-----------------------------------|-----------------------------------|---------|
|                    |                                  | Complete:
yyyymmdd     |                           | Partial:
yyyymm                  |                                     | Partial:
yyyy                  |                                   |         |
|                    |                                  | < 1 st
dose | ≥ 1 st
dose | < 1 st
dose
yyyymm | ≥ 1 st
dose
yyyymm | < 1 st
dose
yyyy | ≥ 1 st
dose
yyyy |         |
| Partial:
yyyymm | = 1 st dose
yyyymm | 2                         | 1                         | 2                                   | 1                                   | n/a                               | 1                                 | 1       |
|                    | ≠ 1 st dose
yyyymm |                           | 2                         |                                     | 2                                   | 2                                 | 2                                 | 2       |
| Partial:
yyyy   | = 1 st dose
yyyy   | 3                         | 1                         | 3                                   | 1                                   | n/a                               | 1                                 | 1       |
|                    | ≠ 1 st dose
yyyy   |                           | 3                         |                                     | 3                                   | 3                                 | 3                                 | 3       |
| Missing            |                                  | 4                         | 1                         | 4                                   | 1                                   | 4                                 | 1                                 | 1       |

1 = Impute the date of first dose

2 = Impute the first of the month

3 = Impute January 1 of the year

4 = Impute January 1 of the stop year

Note: If the start date imputation leads to a start date that is after the stop date, then do not impute the start date.

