## 6.11 Excluded Treatments and/or Procedures During Study Period

The following medications are not permitted during a subject's participation during treatment phase (including the induction and consolidation phases of treatment) of this study:

- Tyrosine kinase inhibitor therapy (eg, imatinib, dasatinib, niolotinib, bosutinib, and ponatinib) are not permitted during treatment with blinatumomab
- Any anti-tumor therapy other than the blinatumomab:
  - Cytotoxic and/or cytostatic drugs
  - Radiation therapy
  - Immunotherapy
- Chronic systemic (> 7 days) high-dose corticosteroid therapy (dexamethasone > 24 mg/day or equivalent)
- Any other immunosuppressive therapies (except for transient use of corticosteroids)
- Any other investigational agent

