### 7.2.5 Long-term Follow-up

Long-term follow-up is required for subjects participating in the Phase 1b/2 parts of the study. Long-term follow-up is not required for subjects participating in the expansion cohort. All subjects enrolled in Phase 1b/2 will be followed in the long-term follow-up portion of the study for survival. Subjects in remission will also be followed for duration of response. Following the safety follow-up visit, subjects will be followed via clinic or telephone contact at 3, 6, 9, 12, 18, and 24 months (± 2 weeks) after completion of the safety follow-up to assess disease status and survival. Subjects will allow Amgen/AABP continued access to medical records, so that information related to subjects' health condition including duration of response and survival may be obtained.

The following procedures will be completed for subjects who remain in remission at each clinic visit:

- Disease/survival status
- Bone marrow aspirate/biopsy (morphological)
- Local laboratory assessments including:
  - Hematology with differential
- Central laboratory assessments including:
  - Lymphocyte subsets (at 6 months after the safety follow-up visit if B cells have not recovered at the safety follow-up visit [ie, number of CD19-positive cells is 90 to 570 per µL])
- Documentation of concomitant medications (anti-leukemic treatments only)

Page 73 of 122

Product: Blinatumomab Protocol Number: 20130265 Date: 20 March 2019

The following procedures will be completed for subjects who did not respond to or relapsed after blinatumomab, who have received other anti-leukemic treatments or HSCT, and are being followed in long-term follow-up:

Telephone contact by either the research investigational site or treating physician to the subject to determine survival status

Documentation of concomitant medications (anti-leukemic treatments only)

Should a subject fail to return to the clinic for a scheduled protocol visit, or not be available for telephone contact, sites will need to make 3 attempts by a combination of telephone and mail to contact subjects. Sites must document all 3 attempts to contact the subject. If a subject does not respond within 1 month after the third contact the subject will be considered lost to follow-up and no additional contact will be required.

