#### **10.7.6 Exposure to Concomitant Medication**

The number and proportion of subjects receiving concomitant medications from study day 1 through safety follow-up will be summarized by preferred term as coded by the World Health Organization Drug (WHODRUG) dictionary in the SAF. In addition, the

number and proportion of subjects receiving anti-cancer therapies during long term follow-up will be summarized by WHODRUG preferred term for the SAF.

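### SAP Table 7 can date follow-up anti-leukemic therapy to the first blinatumomab dose, so it is classed as concomitant rather than as started in follow-up

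*SAP*

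**What the plan says.** SAP Appendix D opens with "The following data will be imputed using the following algorithm" and lists two data types: adverse events and "Concomitant Medications". It makes no exception for anti-leukemic therapy. The start-date rules are in Table 7, "Imputation Rules for Partial or Missing Start Dates", where the relevant code is "1 = Impute the date of first dose". One check applies to the imputed start: "If the start date imputation leads to a start date that is after the stop date, then do not impute the start date".

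Protocol 7.2.5 places later anti-leukemic therapy among the concomitant medications. Its long-term follow-up procedures include "Documentation of concomitant medications (anti-leukemic treatments only", both for subjects in remission and for those followed by telephone. The footnote to Protocol Table 6 says the same.

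SAP 10.7.6 plans two summaries in the safety set. One covers concomitant medication from study day 1 through safety follow-up. In the other, the "number and proportion of subjects receiving anti-cancer therapies during long term follow-up will be summarized". SAP Table 6, in the same section, uses the start date to separate concomitant medication from medication started during follow-up, with the cut at the end-of-induction visit.

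**The concern.** Moving an uncertain start to the first dose is conservative for an adverse event, because it keeps the event treatment-emergent. For a salvage drug first reported after blinatumomab has ended, the same rule gives a date that contradicts the order of events. Protocol 6.6 and 7.2.4 place the safety follow-up visit before any new anti-leukemic treatment.

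The stakes are in the descriptive medication tables. Salvage therapy dated to day 1 would appear alongside blinatumomab and could be missing from the table meant to show what subjects received afterwards. In the derived data it would also resemble the class that Protocol 6.11 excludes during treatment: "Any anti-tumor therapy other than the blinatumomab". Partial dates are plausible here, because for non-responders and relapsed subjects the information comes by telephone.

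**Working it through.** The plan states no figure to reproduce. The check is to read Table 7 for the relevant rows and follow the result forward.

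**Step 1. Table 7 codes, by form of the stop date.**

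| Start date | Full, before first dose | Full, on/after | Month, before | Month, on/after | Year, before | Year, on/after | Missing |
|---|---|---|---|---|---|---|---|
| Year only, same as first-dose year | 3 | 1 | 3 | 1 | n/a | 1 | 1 |
| Wholly missing | 4 | 1 | 4 | 1 | 4 | 1 | 1 |

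**Step 2. Cells that follow-up therapy can reach.** A therapy begun after blinatumomab cannot have stopped before the first dose. That leaves four columns: the three on/after columns and the missing column. Both rows read 1, 1, 1, 1 there, so 2 × 4 = 8 of 8 reachable cells give the date of first dose.

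**Step 3. The safeguard.** It acts only if the imputed start is later than the stop. The imputed start is the first dose, and in these cells the stop is on or after first dose or is missing, so the check does not act. Nothing compares the imputed start with the last dose, the safety visit or the collection period.

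**Step 4. Classification.** Table 6 calls a medication concomitant if it starts by the end-of-induction visit and stops after the first infusion. Follow-up therapy dated to day 1 meets that definition and fails the one for medication started during follow-up.

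**Step 5. Size of the shift (illustration).** Suppose therapy truly begins the day after a safety visit held 30 days after the last dose. With *c* cycles of 42 days, of which 28 are infusion, and uninterrupted treatment, the lag from first dose is D = 42(*c* − 1) + 28 + 30 + 1 days. If first doses are spread evenly over the calendar year (an assumption), the chance that the therapy starts in the first-dose year is 1 − D/365.25.

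| Cycles | D, days moved back | Chance of same year |
|---|---|---|
| 1 | 28 + 31 = 59 | 1 − 59/365.25 = 0.84 |
| 2 | 42 + 59 = 101 | 1 − 101/365.25 = 0.72 |
| 5 | 168 + 59 = 227 | 1 − 227/365.25 = 0.38 |

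For example, with an assumed first dose on 15 March 2016 and two cycles, therapy begins on 24 June 2016. If it is reported only as 2016, its derived start is 15 March 2016. A wholly missing start goes to day 1 whatever the year.

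**Step 6. Weight of one subject.** Long-term follow-up applies to Phase 1b/2 only, at most 57 subjects, 21 of them in Phase 2. One misplaced subject moves a proportion by 1/21 = 4.8 percentage points in Phase 2, or 1/57 = 1.8 points if all were taken together. Adults and children are tabulated separately, so actual denominators are smaller than 57.

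**The case against.** The best case against has four parts.

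- **Appendix D is only the general rule.** SAP 9.3 says the algorithm will be described in a Data Definition Table, which may treat follow-up therapy separately, and that imputed dates go to derived datasets, not raw data. Both statements are correct. However, the SAP sets the rule and exempts nothing, and the derived datasets are where the harm would arise.
- **Loss from the follow-up table is not certain.** A reader might infer that the subject must drop out of it. SAP 10.7.6 counts subjects receiving therapy during long-term follow-up and does not say whether the period is set by derived start date or by collection period. An ongoing therapy dated to day 1 still overlaps follow-up. The omission is therefore conditional.
- **Wider harm is not shown.** A reader might infer a false deviation that removes the subject from the per-protocol set. SAP 10.3 decides exclusions patient by patient with documented reasons, the raw year-only date would be visible, and the per-protocol repeat is optional. A reader might also infer that OS is distorted. OS uses death or last contact, and its optional sensitivity analysis censors at HSCT. No primary, OS, RFS or TTHR analysis uses the start date of anti-leukemic drug therapy.
- **Frequency is unknown.** No document gives the share of year-only or missing starts, so a percentage of misplaced therapies would rest on an invented input. Follow-up contacts every 3 months in the first year and access to medical records make such dates less likely.

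These points limit the consequence. They do not change the date that the stated rule produces.

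**Conclusion.** The point holds as a minor error in a stated rule. For follow-up anti-leukemic therapy with a start known only as the first-dose year, or not at all, Table 7 gives the first-dose date in every cell the therapy can reach, and Table 6 then puts it in the wrong class. It can be wrongly counted in the summary from day 1 to safety follow-up. Its omission from the follow-up anti-cancer summary depends on that table using derived start dates.

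The shift equals the full lag from first dose. The 59, 101 and 227 days assume uninterrupted cycles and therapy starting the day after the safety visit; the same-year chances also assume evenly spread first doses. The effect is confined to descriptive medication tables in Phase 1b/2. The expansion cohort has no long-term follow-up.

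**What to change.** Add to SAP Appendix D: for anti-leukemic therapies first reported in the long-term follow-up collection period, with a year-only or wholly missing start, impute no earlier than the day after the safety follow-up visit, or the day after the last blinatumomab dose if there was no visit. The imputed date stays within any known year, and the existing stop-date check still applies.

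Three limits keep this from creating new errors:

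- A known month is kept, as code 2 now does.
- Therapies reported at or before the safety visit stay under Table 7, so therapy truly given during treatment is not hidden.
- HSCT is left out, because Appendix D does not list it.

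In 10.7.6, state that the follow-up anti-cancer summary is assigned by collection period.

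The cost is a few lines of SAP text and the matching programming. Adverse-event imputation is untouched. There is one downside: a therapy truly started shortly before the safety visit, but first reported later with only the year known, would be dated slightly late.

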**Imputation rules for partial or missing stop dates:**

Initial imputation

For partial stop date mmyyyy, impute the last of the month.

For partial stop date yyyy, impute December 31 of the year.

For completely missing stop date, do not impute.

If the stop date imputation leads to a stop date that is after the death date, then impute the stop date as the death date.

If the stop date imputation leads to a stop date that is before the start date, then there is a data error and do not impute the stop date. (ie, set the stop date as missing).

**Imputation rules for partial or missing death dates:**

If death year and month are available but day is missing:

If mmyyyy for last contact date = mmyyyy for death date, set death date to the day after the last contact date.

If mmyyyy for last contact date < mmyyyy for death date, set death date to the first day of the death month.

If mmyyyy for last contact date > mmyyyy for death date, data error and do not impute.

If both month and day are missing for death date or a death date is totally missing, do not impute.
